6.2 Nonserious Adverse Events

A *nonserious adverse event* is an AE not classified as serious.

6.2.1 Nonserious Adverse Event Collection and Reporting

The collection of nonserious AE information should begin at initiation of study drug until 100 days from the last dose of study drug. Nonserious AE information should also be collected from the start of a placebo lead-in period or other observational period intended to establish a baseline status for the subjects.

Nonserious AEs should be followed to resolution or stabilization, or reported as SAEs if they become serious (see [Section 6.1.1](#)). Follow-up is also required for nonserious AEs that cause interruption or discontinuation of study drug and for those present at the end of study treatment as appropriate. All identified nonserious AEs must be recorded and described on the nonserious AE page of the CRF (paper or electronic).

Completion of supplemental CRFs may be requested for AEs and/or laboratory abnormalities that are reported/identified during the course of the study.

6.3 Laboratory Test Result Abnormalities

The following laboratory test result abnormalities should be captured on the nonserious AE CRF page or SAE Report Form electronic) as appropriate. Paper forms are only intended as a back-up option when the electronic system is not functioning.

- Any laboratory test result that is clinically significant or meets the definition of an SAE
- Any laboratory test result abnormality that required the subject to have study drug discontinued or interrupted
- Any laboratory test result abnormality that required the subject to receive specific corrective therapy

It is expected that wherever possible, the clinical rather than laboratory term would be used by the reporting investigator (eg, anemia versus low hemoglobin value).

6.4 Pregnancy

If, following initiation of the study drug , it is subsequently discovered that a study subject is pregnant or may have been pregnant at the time of study exposure, including during at least time to washout plus one ovulatory cycle (30 days) for a total of 23 weeks, or plus one spermatogenesis cycle (90 days) for a total of 31 weeks after product administration (for patients in arms A and C; 4 week duration needed for arm B), the investigator must immediately notify the BMS Medical Monitor/designee of this event and complete and forward a Pregnancy Surveillance Form to BMS Designee within 24 hours of awareness of the event and in accordance with SAE reporting procedures described in [Section 6.1.1](#). Refer to pomalidomide pregnancy risk prevention plan for additional information ([Appendix 6](#)).

In most cases, the study drug will be permanently discontinued in an appropriate manner (eg, dose tapering if necessary for subject safety). Please call the BMS Medical Monitor within 24 hours of awareness of the pregnancy.

The investigator must immediately notify the BMS (or designee) Medical Monitor of this event and complete and forward a Pregnancy Surveillance Form to BMS (or designee) within 24 hours of awareness of the event and in accordance with SAE reporting procedures described in [Section 6.1.1](#).

Follow-up information regarding the course of the pregnancy, including perinatal and neonatal outcome and, where applicable, offspring information must be reported on the Pregnancy Surveillance Form.

Any pregnancy that occurs in a female partner of a male study participant should be reported to BMS. Information on this pregnancy will be collected on the Pregnancy Surveillance Form.

6.5 Overdose

An overdose is defined as the accidental or intentional administration of any dose of a product that is considered both excessive and medically important. All occurrences of overdose must be reported as an SAE (see [Section 6.1.1](#) for reporting details.).

Of note, doses up to 20mg/kg of elotuzumab and doses of up to 10mg/kg of nivolumab have been safely administered in prior studies.

6.6 Potential Drug Induced Liver Injury (DILI)

Wherever possible, timely confirmation of initial liver-related laboratory abnormalities should occur prior to the reporting of a potential DILI event. All occurrences of potential DILIs, meeting the defined criteria, must be reported as SAEs (see [Section 6.1.1](#) for reporting details).

Potential drug induced liver injury is defined as:

1. AT (ALT or AST) elevation > 3 times upper limit of normal (ULN)
AND
2. Total bilirubin > 2 times ULN, without initial findings of cholestasis (elevated serum alkaline phosphatase)
AND
3. No other immediately apparent possible causes of AT elevation and hyperbilirubinemia, including, but not limited to, viral hepatitis, pre-existing chronic or acute liver disease, or the administration of other drug(s) known to be hepatotoxic.

6.7 Other Safety Considerations

Any significant worsening noted during interim or final physical examinations, electrocardiogram, x-ray filming, any other potential safety assessment required or not required by protocol should also be recorded as a nonserious or serious AE, as appropriate, and reported accordingly.

Second primary malignancies (SPMs) will be collected throughout the study which includes assessments during survival follow-up. All SPMs that occur during the screening period and within 60 days of discontinuation of dosing will be reported as an SAE regardless of relationship to study drug. Additionally, any SPM that occurs after this timeframe and considered related to study drug will be reported as an SAE. All other SPMs will be collected and reported on a separate CRF page.

Immune-mediated adverse events (IMAEs) are AEs consistent with an immune-mediated mechanism or immune-mediated component for which non-inflammatory etiologies (eg, infection or tumor progression) have been ruled out. IMAEs can include events with an alternate etiology which were exacerbated by the induction of autoimmunity. Information supporting the assessment will be collected on the subject's case report form.

7 DATA MONITORING COMMITTEE AND OTHER EXTERNAL COMMITTEES

An independent data monitoring committee (DMC) will be established before the first subject is treated to provide oversight of safety and study conduct. The DMC will review safety and efficacy data at periodic intervals.

The first comprehensive safety review will occur after the first 42 treated subjects (ie, the first 6 subjects in the exploratory arm) have been followed for 1 month

An independent review committee (IRC) had been set up to review blinded responses and progression criteria in each subject. However, after enrollment was discontinued, it was decided to discontinue efficacy assessment by IRC.

Separate charters will provide further guidance and describe the activities of these committees.

8 STATISTICAL CONSIDERATIONS

8.1 Sample Size Determination

Prior to Revised Protocol 02, the study planned to randomize 406 subjects at a 3:3:1 ratio to N-Pd vs Pd vs NE-Pd. Also, subjects randomized to the Pd control arm were allowed to cross-over to the exploratory NE-Pd arm upon progression. As of 1 September 2017, cross-over was no longer permitted and as of Revised Protocol 02, the exploratory NE-Pd arm was closed to enrollment.

In Revised Protocol 02, the planned sample size for this study was revised to approximately 348 randomized subjects randomized at a 1:1 ratio to N-Pd vs Pd. The sample size of the study accounts for the primary efficacy endpoint of PFS. PFS will be evaluated for treatment effect at the overall alpha level of 0.05 (two-sided) with 90% power with two interim analyses, with the first one for early futility and the second for efficacy.

- The study requires at least 262 PFS events to ensure that a two-sided 5% type I error sequential test procedure with two interim analyses will have 90% power to detect a hazard ratio (HR) of 0.667, corresponding to a median PFS of 6 vs 4 months for the N-Pd and Pd arms, respectively.

East version 6.3 was used for sample size/power computation.

Table 8.1-1: Schedule of Analyses

	Interim analysis for PFS	Final analysis for PFS
Condition for PFS	Interim 1: at least 131 PFS events (for futility only)	at least 262 PFS events
	Interim 2: at least 184 PFS events (for efficacy only)	
Expected timing	Interim 1: 8 months after enrollment is reopened	22 months after enrollment is re-opened
	Interim 2: 16 months after enrollment is re-opened	

Table 8.1-1: Schedule of Analyses

	Interim analysis for PFS	Final analysis for PFS
Alpha Level	Interim 1: Futility boundary on HR 1.053	Final PFS at 0.0456 level ^a
	Interim 2: PFS at 0.0148 level ^a	

^a Using Lan-DeMets α spending function with O'Brien and Fleming type of boundary when exactly 184 PFS events are observed at the interim analysis for PFS.

On 23-August-2018, the Sponsor (BMS) decided to permanently discontinue enrollment based on insufficient clinical benefit observed at an interim futility analysis for PFS. A total of 170 subjects had been randomized in the study.

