As of 23-August-2018, the further enrollment of CA209602 study was permanently closed due to the insufficient benefit observed based on the interim futility analysis of PFS. A total of 170 subjects were randomized into the study: 75 to NPd, 71 to Pd and 24 to NE-Pd arms. Subjects randomized to the NPd or NEPd arms may continue treatment based on investigator's judgement of continued clinical benefit. Study will be closed after all subjects complete safety follow-up (i.e., 100 days after the last subject has discontinued study treatment).

The study design schematic is presented below:

Study Population: Subjects who are diagnosed with refractory or relapsed multiple myeloma defined as:

1. Must have received ≥ 2 prior lines of therapy which must have included an immune modulatory drug (IMiD) and a proteasome inhibitor (PI) alone or in combination. Subject must have received at least 2 consecutive cycles of an IMiD and at least 2 consecutive cycles of a PI. The dose of the prior IMiD (eg, lenalidomide) to which the subject has relapsed or been refractory must be the induction dose and NOT a maintenance dose (Note: adjusted induction dose for intolerance reasons or for renal impairment is accepted).
2. Documented refractory or relapsed and refractory (R/R) multiple myeloma
3. Refractory (lack of response or progressed on or within 60 days of the last dose of treatment) to their last line of treatment. Lack of response is defined as not having achieved at least PR.¹
4. Subjects must have failed treatment with a proteasome inhibitor and an IMiD in one of the following ways:
 - a. **“Refractory”** = Refractory (lack of response or progressed on treatment or within 60 days of the last dose of treatment, regardless of the achievement of initial response) to a proteasome inhibitor and an IMiD. Lack of response is defined as not having achieved at least PR.¹

- b. "Relapsed and refractory"= patients had achieved at least a partial response to previous treatment with proteasome inhibitor or IMiD or both but then progressed after 60 days of the last dose of treatment.
- 5. Have measurable disease
- 6. Meet all eligibility criteria in [Section 3.3](#)

Study Drug: includes both Investigational [Medicinal] Products (IP/IMP) and Non-investigational [Medicinal] Products (Non-IP/Non-IMP) as listed:

Study Drug for CA209602		
Medication	Potency	IP/Non-IP
Nivolumab	100 mg (10 mg/mL)	IP
Elotuzumab	400mg/vial	IP
Pomalidomide Capsules	1 mg, 2 mg, 3 mg and 4 mg	Non-IP

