Dexamethasone Tablets	2 mg and 4 mg & various strengths	Non-IP
Dexamethasone Solution	4 mg/mL, 8 mg/mL & various strengths	Non-IP

Study Assessments: Tumor response assessment by IMWG criteria will be evaluated during the trial for all randomized subjects. The primary endpoint PFS will be based on the investigator.

Statistical Considerations:

Sample Size:

In Revised Protocol 02, the planned sample size for this study was revised to approximately 348 randomized subjects randomized at a 1:1 ratio to N-Pd vs Pd. The sample size of the study accounts for the primary efficacy endpoint of PFS. PFS will be evaluated for treatment effect at the overall alpha level of 0.05 (two-sided) with 90% power with two interim analyses, with the first one for early futility and the second for efficacy.

The study requires at least 262 PFS events to ensure that a two-sided 5% type I error sequential test procedure with two interim analyses will have 90% power to detect a hazard ratio (HR) of 0.667, corresponding to a median PFS of 6 vs 4 months for the N-Pd and Pd arms, respectively.

On 23-August-2018, the Sponsor (BMS) decided to permanently discontinue enrollment based on insufficient clinical benefit observed at an interim futility analysis for PFS. A total of 170 subjects have been randomized in the study.

Endpoints:

Primary Endpoints:

The primary objective in the study will be measured by the primary endpoint PFS by investigator within the N-Pd and Pd arms.

Secondary Endpoints:

The secondary objectives in the study will be measured by

- OS
- ORR
- TTR
- DOR

Analyses:

PFS Analysis Timepoints

- At the time of PFS analyses, as assessed by investigator, the distribution of PFS in N-Pd group will be compared with the Pd arm via a two-sided, log-rank test stratified by prior lines of therapy and ISS stage at study entry. The hazard ratio (HR) and the corresponding 100x(1-adjusted alpha)% confidence interval (CI) will be estimated in a stratified Cox proportional hazards model using treatment as a single covariate.
- PFS curves, PFS medians with two-sided 95% CIs, and PFS rates at at select milestone with 95% CIs will be estimated using Kaplan-Meier methodology.

Analysis of OS

- At the time of PFS analyses, OS will be summarized by the Kaplan-Meier product limit method within each arm. Median values along with two-sided 95% CIs based on the log log transformation, will be calculated. Additional details of OS analysis will be included in the SAP

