3 INVESTIGATIONAL PLAN

3.1 Study Design and Duration

This is a phase 3 multicenter, randomized, open label study designed to evaluate the clinical benefit and safety of the combination therapy of Nivolumab, pomalidomide, and dexamethasone (N-Pd the investigational arm A), when compared to pomalidomide and dexamethasone (Pd; the control arm B) in subjects with relapsed and/or refractory multiple myeloma (rrMM).

Up to Revised Protocol 01, the study design included an exploratory third arm evaluating the clinical benefit and the safety of the combination therapy of elotuzumab, nivolumab, pomalidomide and dexamethasone (NE-Pd, the exploratory arm-[arm C]) in the same patient population. Additionally, subjects randomized to the Pd arm were allowed to cross over to this exploratory NE-Pd arm at the time of progression. Cross over was stopped as of 1 September 2017.

Enrollment in the NE-Pd exploratory arm was stopped as of Revised Protocol 02. All subjects already randomized to the NE-Pd arm, or who crossed over from the Pd to the NE-Pd arm will continue on study as long as they have clinical benefit and do not meet the study discontinuation criteria.

[figure not shown]
Initially, the study was designed to enroll approximately 417 subjects for a total of 348 subjects to be randomized (assuming 20% screen failure rate) to N-Pd and Pd arms in a 1:1 ratio. Randomization was performed with the following stratification factors: a) number of lines of prior therapy (2 vs 3+); AND b) ISS stage (1-2 vs 3).

Subjects were to continue treatment as long as the subject has clinical benefit from the treatment and does not meet criteria for treatment discontinuation.

As of 23-August-2018, any additional enrollment of CA209602 study was permanently closed due to the insufficient benefit observed based on the interim futility analysis of PFS. A total of 170 subjects were randomized into the study: 75 to NPd, 71 to Pd and 24 to NE-Pd arms. Subjects randomized to the NPd or NEPd arms may continue treatment based on investigator's judgement of continued clinical benefit. Study will be closed after all subjects complete safety follow-up (i.e., 100 days after the last subject has discontinued study treatment).

The study design schematic is presented in Figure 3.1-1.

Figure 3.1-1: Study Design Schematic

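### The 262-event, 90%-power PFS design is not withdrawn although the closed trial can yield at most 146 events, and the adjusted-alpha CI has numeric levels only from a look that cannot occur

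*Combined protocol and SAP*

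**What the plan says.** Section 8.1 and the synopsis (Sample Size) introduce the 348-subject, 1:1 plan as that of Revised Protocol 02 and then continue in the future and present tense: "PFS will be evaluated for treatment effect at the overall alpha level of 0.05 (two-sided) with 90% power with two interim analyses", and "The study requires at least 262 PFS events to ensure that a two-sided 5% type I error sequential test procedure" has 90% power at HR 0.667 (median PFS 6 versus 4 months).

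Table 8.1-1, in Section 8.1 only, lists three looks:
- a futility look at 131 events;
- an efficacy look, "Interim 2: at least 184 PFS events (for efficacy only"), at the 0.0148 level;
- a final analysis at 262 events, "Final PFS at 0.0456 level".

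Its footnote says that the two levels apply "when exactly 184 PFS events are observed at the interim analysis for PFS".

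On the current state of the trial, the synopsis says "As of 23-August-2018, the further enrollment of CA209602 study was permanently closed", and Section 3.1 says "A total of 170 subjects were randomized into the study: 75 to NPd, 71 to Pd and 24 to NE-Pd arms". Section 8.1 repeats the enrolment stop but gives only the total of 170. Section 8.4 ties the main analysis to the end of the last subject's safety follow-up, with no event condition. Section 8.5 describes the futility analysis that was performed.

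For the primary estimate, Section 8.4.2.1 and the synopsis both say "The hazard ratio (HR) and the corresponding 100x(1-adjusted alpha)% confidence interval (CI) will be estimated" from a stratified Cox model. Neither gives a number for the adjusted alpha. Details of testing are left to the SAP, whose text is not in the supplied document.

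**The concern.** PFS by investigator is still the primary objective and still receives a formal stratified log-rank test. Nothing in Section 8.1 or the synopsis withdraws the event requirement, the power or the alpha schedule, and neither place says what power the closed trial can have. A reader who takes the stated 90% at face value would give a non-significant PFS result more weight as evidence against the design effect than the trial can support.

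There is a smaller, linked gap. The confidence level for the primary hazard ratio points to an adjusted alpha, and the only numbers available for it come from a group-sequential schedule that can no longer be followed.

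**Working it through.** **Inputs.** HR 0.667, two-sided 0.05, 90% power, 262 events, looks at 184 (0.0148) and 262 (0.0456): Section 8.1 and Table 8.1-1. Arm sizes 75 N-Pd and 71 Pd: Section 3.1 and the synopsis. The final event count is not given, so a range is assumed below.

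**1. The plan's own figure.**
- Schoenfeld, fixed design, 1:1: 4 × (1.960 + 1.282)² / (ln 0.667)² = 257 events. Freedman's formula gives 264.
- Group-sequential calculation with looks at 184 and 262 events and O'Brien-Fleming-type Lan-DeMets spending: power at 262 events is 90.2%.
- The printed levels 0.0148 and 0.0456 at these two looks give an overall two-sided type I error of 0.0501.

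The 262-event requirement is therefore reproduced. It was sound while enrolment was expected to continue.

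**2. The ceiling on events.** Each subject contributes at most one PFS event.
- Maximum: 75 + 71 = 146, which is 146/262 = 55.7% of the requirement.
- Shortfall: 184 − 146 = 38 and 262 − 146 = 116.
- Even all 170 randomized subjects, including the 24 on NE-Pd who are not in the comparison, would not reach 184.

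The count will probably fall below 146, because Section 8.3.1.1 censors subjects who start subsequent therapy without a reported progression.

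**3. Power at reachable counts.** With d events and 75:71 allocation, power = Φ(|ln 0.667| × √(d × 75 × 71 / 146²) − 1.960). Here |ln 0.667| = 0.405 and 75 × 71 / 146² = 0.2498.

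| Events d | Basis | Power at HR 0.667 |
|---|---|---|
| 146 | all subjects have an event (ceiling) | 68.6% |
| 131 | assumed 90% | 63.9% |
| 117 | assumed 80% | 59.1% |
| 102 | assumed 70% | 53.4% |

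Worked line for d = 146: √(146 × 0.2498) = 6.039; 0.405 × 6.039 = 2.446; 2.446 − 1.960 = 0.486; Φ(0.486) = 68.6%.

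The HR detectable with 90% power at 146 events is exp(−(1.960 + 1.282)/6.039) = 0.585, against the design value of 0.667.

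**4. Size of the confidence-level gap at 146 events.**

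| Level | z | Half-width on log HR (z/6.039) | Critical HR |
|---|---|---|---|
| 0.05 | 1.960 | 0.325 | 0.723 |
| 0.0456 | 1.999 | 0.331 | 0.718 |

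The ratio 1.999/1.960 = 1.020, so the interval on the log scale is 2.0% wider at 0.0456.

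**The case against.** The strongest reply is that this is design history in the wrong tense. The paragraph opens by naming Revised Protocol 02, both places go on to report the enrolment stop, the table's timings run from a reopening of enrolment, and the synopsis and Section 3.1 put the 348-subject plan in the past. Section 8.4 already sets the analysis time. The SAP may fix the alpha level. The trial stopped for insufficient benefit, so few readers would take a null result as a 90%-powered negative.

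Much of that stands. A reader might infer that looks at 184 and 262 events are still intended; Section 8.4 and the disclosed closure do not support this. A reader might also see a contradiction between the table's futility look (131 events, HR 1.053) and Section 8.5 (85 events assumed, HR 0.995). Section 8.5 describes a separate look, requested by the FDA on 21 June 2018, after Revised Protocol 02 of 22 May 2018, with its own criterion set beforehand, so the difference is not in itself an error. Nor should the 85 events be used as a scenario for the final analysis: that was a planning count for an April 2018 database lock, and follow-up continued.

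It is also fair that 69% is an unconditional figure, which takes no account of the interim result, and it should be labelled so.

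What does not fall away is that the event requirement, the power and the alpha levels are never withdrawn, and the attainable power is nowhere given. A SAP could settle the confidence level, but it would not correct the power stated in the protocol.

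**Conclusion.** The point holds as a failure to retire a superseded design, and it should be fixed. The protocol leaves standing a 90% power and a 262-event requirement that 146 subjects cannot deliver. Power at HR 0.667 is at most about 69%, and about 53% to 64% if 70% to 90% of subjects have events. This rests on the Schoenfeld approximation, 75:71 allocation, two-sided 0.05 and no conditioning on the interim data. The 146-event ceiling is arithmetic on the protocol's own counts; the 70% to 90% event fractions are assumptions.

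The confidence-level issue is minor and provisional on the SAP. A reader might infer that the final test or interval would be invalid. The documents do not support that: the only formal PFS look described was for futility, and applying 0.0456 would be slightly conservative, with an interval about 2% wider. Nor does anything here show a miscalculation in the Revised Protocol 02 design, or a need to recast the primary comparison as descriptive.

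**What to change.** 1. In Section 8.1, Table 8.1-1 and the synopsis, label the 262-event, 90%-power design and its schedule of looks as the superseded Revised Protocol 02 design.
2. Beside it, state that the compared arms can yield at most 146 PFS events, so that power at HR 0.667 is at most about 69% (unconditional, two-sided 0.05) and lower with fewer events.
3. Refer to Section 8.4 for the single final PFS analysis and to Section 8.5 for the futility look performed.
4. Unless the SAP already fixes the level, replace the adjusted alpha in Section 8.4.2.1 and the synopsis with two-sided 0.05 and a 95% CI, because the only formal PFS look described was for futility. Keep protocol and SAP consistent on this, and settle it before the final database lock.

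Items 1 to 3 change wording only. Item 4 names a level that the supplied text leaves open, so it should be recorded as a decision. No data, analysis set or procedure changes. The price is a less favourable stated power.
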